4.4 Sample size calculation

Provisional calculations show that a power of 90% to detect a 10% reduction in antibiotic use (from 55% to 45%) at a statistical significance level of 0.05 is achievable with the available resources resulting in recruitment of approximately 1046 children, 523 in each arm. With an expected dropout rate of 15% we aim to include 1204 children in total, 602 in each arm.

We expect to be able to include a sufficient number of patients in approximately three months. Each clinic has a patient flow of approximately 10 – 25 children per week. With 14 clinics, the weekly flow of potential participants is 100 – 250 even if only less than 1 in 2 patients are enrolled; we will still keep our schedule.

There has not been a diminished flow of patients at the healthcare centres during the COVID-19 pandemic, so the study should be able to move ahead on schedule even in the face of the pandemic.

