7.16 Power calculation

As the study employs a combined superiority and non-inferiority approach based on the two related primary study outcomes; we provide two power calculations and opt for the conservative number of participants to ensure the adequate sample size for answering both primary outcomes. Power calculations are performed using sample size calculators provided by Sealed Envelope™.

Superiority power calculations show that for a power of 90% to detect a 10% reduction in antibiotic use (from 55% to 45% based on previous pilot registrations in the area) at a statistical significance level of 0.05 a total of 1046 children, 523 in each arm are necessary.

In our non-inferiority power calculation, we apply a margin of non-inferiority of one day (24 hours), i.e. the intervention arm is allowed to have a mean time to recovery that is one day longer than the mean recovery time in the control arm without being deemed inferior. The duration of acute respiratory tract infection in children is approximately 7 days with a standard deviation of 5 days. Hence, for a power of 90% and a statistical significance level of 0.05 a total of 858 children are needed.

To be able to assess both outcomes we will opt for the conservative measure, e.g. the superiority measure.

With an expected dropout rate of 15% we aim to include 1204 children in total, 602 in each arm. This is deemed achievable with the available resources. We expect to be able to include a sufficient number of patients in approximately three months. Each clinic has a patient flow of approximately 10 – 25 children per week. With 10 clinics, the weekly flow of potential participants is 100 – 250 even if only less than 1 in 2 patients are enrolled; we will still keep this schedule.

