7.19 Analysis of main outcomes

The main superiority outcome of antibiotic reductions at day 14 will be assessed by a multivariate logistic regression model and results presented both as odds ratio and as the absolute risk difference of antibiotic exposure in the two study arms. This analysis will be done as intention to treat (ITT).

The main non-inferiority outcome of patient safety will be assessed by a multivariate, generalised, linear model to calculate an adjusted 95% confidence interval (CI) for the

COORDINATE

difference between CRP-guided and standard therapy in the number of days until recovery. This analysis will both be done as ITT and per-protocol (PP).

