7.20 Missing data and lost to follow up

To correct for potential differences in between the groups with regard to missing data and patients that are lost to follow up the main analysis will be done with inverse probability weighing (IPW).

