7.21 Analysis of secondary outcomes

Antibiotic treatment at follow up

Using linear regression we will compare how many in the intervention and non-intervention group are prescribed antibiotics at the index consultation.

Antiviral treatment at follow up

Using linear regression we will compare how many in the intervention and non-intervention group start antiviral treatment (prescribed or bought over-the-counter) within 14 days after the index consultation.

Reconsultations

Using linear regression we will compare how many in the intervention and non-intervention group come for reconsultations (planned and unplanned) within 14 days after the index consultation.

Hospital referral at index consultation

Using linear regression we will compare how many in the intervention and non-intervention group are referred to hospital at the index consultation.

Hospital admission at follow up

Using linear regression we will compare how many in the intervention and non-intervention group are or have been admitted into hospital until day 14 after the index consultation.

Mortality

Using linear regression we will compare mortality status in the intervention and non-intervention group.

Secondary outcomes will be expressed with 95% two-sided confidence intervals.

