7.22 Adjustment for baseline variables

The analyses of the outcomes will be adjusted for the stratification variables – age and sex – so as to boost the power of the analyses. Additionally, clinical relevant variables such as respiratory frequency, fever and other severity markers will be included.

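### Section 7.16: the non-inferiority figure of 858 is a one-sided 5% result set against a 95% CI, and the 15% dropout is multiplied in rather than divided out; both have a small effect at 1204

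*Combined protocol and SAP*

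**What the plan says.** The trial has two primary outcomes: antibiotic prescription within 14 days (superiority) and days until recovery (non-inferiority). Section 7.16 of the combined protocol and SAP gives a calculation for each, both at 90% power.

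- Superiority, 55% against 45%: "at a statistical significance level of 0.05 a total of 1046 children, 523 in each arm are necessary".
- Non-inferiority, margin one day, SD 5 days: "Hence, for a power of 90% and a statistical significance level of 0.05 a total of 858 children are needed".

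Neither calculation says whether 0.05 is one-sided or two-sided. The section then chooses between them: "To be able to assess both outcomes we will opt for the conservative measure, e.g. the superiority measure".

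The recruitment target is the same in sections 4.4 and 7.16: "With an expected dropout rate of 15% we aim to include 1204 children in total, 602 in each arm".

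For the analysis, section 7.19 uses a generalised linear model "to calculate an adjusted 95% confidence interval (CI) for the" difference in days to recovery, under both ITT and per protocol. It does not give the sidedness of that interval. The only statement of sidedness is in section 7.21 and concerns other endpoints: "Secondary outcomes will be expressed with 95% two-sided confidence intervals".

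**The concern.** One significance level appears to stand for two different tests, and the non-inferiority test that was sized may not be the one that will be run. As printed, non-inferiority needs 188 fewer children than superiority (1046 − 858). A reader would take that as room for the safety outcome, including its per-protocol analysis. If the 95% CI is two-sided, that room does not exist.

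The dropout allowance also looks too small. A loss of 15% applies to the number enrolled, so the evaluable requirement should be divided by 0.85, not multiplied by 1.15. What is at stake is the accuracy of the stated 90% power for both primary outcomes. The design is not in question, because the trial is sized on 1046 and 1204, not on 858.

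**Working it through.** **Inputs.** From 7.16: rates 55% and 45%; margin 1 day; SD 5 days; power 90%; alpha 0.05; dropout 15%; 1204 enrolled. From 7.4: 1:1 allocation. Assumption: true difference in mean recovery time of zero, which is not stated but reproduces 858. All figures use the normal approximation, with z = 1.960 (two-sided 5%, or one-sided 2.5%), 1.645 (one-sided 5%) and 1.2816 (90% power).

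**Step 1. Superiority.** Per arm, n = [z·√(2 × 0.5 × 0.5) + 1.2816·√(0.55 × 0.45 + 0.45 × 0.55)]² / 0.10².

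- Two-sided 5%: 523.3, which matches the stated 523.
- One-sided 5%: 426.3, which does not.

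Without pooling the variance, the two-sided result is 520.1, so the choice of formula changes little.

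**Step 2. Non-inferiority.** Per arm, n = 2 × 5² × (z + 1.2816)² / 1².

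- One-sided 5%: 50 × (1.645 + 1.2816)² = 428.2, rounded up to 429, total 858. This is exactly the plan's figure.
- One-sided 2.5%, the tail tested by a two-sided 95% CI: 50 × (1.960 + 1.2816)² = 525.4, rounded up to 526, total 1052.

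So the same 0.05 is two-sided in Step 1 and one-sided in Step 2. With a two-sided interval the non-inferiority requirement (1052) slightly exceeds the superiority requirement (1046). At 858 evaluable children (429 per arm), power with a two-sided 95% CI would be 83.4%.

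**Step 3. Dropout.**

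- The plan's route: 523 × 1.15 = 601.45, rounded up to 602 per arm, total 1204.
- Dividing out: 1046 / 0.85 = 1230.6, so 1231. For 1052: 1052 / 0.85 = 1237.6, so 1238.
- Left after 15% loss from 1204: 1204 × 0.85 = 1023.4, or 511.7 per arm.
- Loss at which 1204 still delivers the requirement: 1 − 1046/1204 = 13.1%, or 1 − 1052/1204 = 12.6%.

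**Step 4. Power at the number actually expected (511.7 per arm).**

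| Outcome | Test | Power |
|---|---|---|
| Superiority | two-sided 5% | 89.3% |
| Non-inferiority | one-sided 2.5% | 89.2% |
| Non-inferiority | one-sided 5% | 94.0% |

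**Step 5. Factors outside the plan's calculation.**

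- Covariate adjustment: for days to recovery, explaining 1 − 511.7/525.4 = 2.6% of the variance would bring non-inferiority back to 90%.
- Inverse probability weighting (7.20) may work in the other direction. The documents give nothing from which to size it.
- Per-protocol exclusions: no rate is given. If a further 5% to 15% were excluded (an assumption), 486.1 to 434.9 per arm would remain, and non-inferiority power at one-sided 2.5% would be 87.7% to 83.9%.

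**The case against.** The best defence is that the first part is an omission rather than an error. Neither 7.16 nor 7.19 gives sidedness, and if a one-sided 95% bound was intended, 858 is correct. That is true, and the conclusion on 858 is conditional for this reason. It does not remove the need to say which was meant: the unqualified 0.05 still denotes two different tests within one section, and no section mentions a one-sided bound or a 90% interval.

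Second, 858 determines nothing. The trial is sized on 1046; the gap to 1052 is six children, and at 523 per arm non-inferiority power is still 89.9% at one-sided 2.5%. Six children is also about the spread between standard superiority formulas (1042 to 1048 in total). This stands. The two requirements are practically equal, and what fails is only the statement that superiority is the conservative choice. Nor does the plan expressly claim a reserve; a reader infers it from 858 against 1046.

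Third, treating every dropout as non-evaluable is a worst case for superiority. A child prescribed an antibiotic at the index visit has already met the endpoint, and that prescription is recorded at inclusion. This softens the effect on superiority. It does not help days to recovery, and it does not make 1204 the right inflation of 1046 under the plan's own 15%.

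Fourth, section 7.22 adjusts for covariates "so as to boost the power of the analyses", and a modest gain would close the gap. This is also true, but the stated 90% does not rely on adjustment, and weighting could offset the gain.

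**Conclusion.** The concern holds, as a minor point. The dropout error needs only the plan's own figures: 1204 less 15% leaves about 1023, below its stated 1046. The non-inferiority mismatch holds if the 95% CI in 7.19 is two-sided, the conventional reading; the required total is then 1052, not 858. On that reading both primary outcomes have about 89% power at the expected evaluable number, each less than one percentage point below 90%. If the interval is one-sided, 858 stands, non-inferiority power is 94.0%, and only the missing sidedness and the dropout step need correcting.

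These figures rest on a zero true difference in recovery time, on all dropouts being non-evaluable, and on no allowance for covariate adjustment or weighting. The per-protocol figures rest on an assumed exclusion rate and show direction only.

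**What to change.** 1. In 7.16, state the sidedness of alpha for each calculation. In 7.19, state the sidedness of the 95% CI that decides non-inferiority. The two sections must agree, and this should be settled before unblinding so that the choice of bound cannot follow the data.
2. If the interval is two-sided, replace 858 with 1052 (526 per arm, one-sided 2.5%). Delete the statement that superiority is the conservative size, and adjust the opening of 7.16, which promises to adopt the larger number; say instead that the two requirements are practically equal. If it is one-sided, keep 858 and say so.
3. In 7.16 and 4.4, keep 1204 but describe it as about 1023 evaluable after 15% loss. With a two-sided interval, give power as about 89% for each primary outcome before covariate adjustment or weighting; with a one-sided bound, give 89.3% for superiority and 94.0% for non-inferiority.
4. Add one sentence that per-protocol exclusions will lower non-inferiority power further.

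The cost is wording in three sections and no additional children. If the investigators prefer to restore 90% at 15% dropout, the target becomes 1231 for superiority alone (1231 − 1204 = 27 more) or 1238 for both outcomes with a two-sided interval (1238 − 1204 = 34 more).

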7.17 Data cleaning and data checking

Before unblinding and analysis the data will be checked for outlying, missing and/or otherwise faulty values. Faulty input and/or extreme outliers will be corrected, and it will be attempted to trace missing values.

7.18 Analysis of baseline variables

An unadjusted comparison will be done between baseline variables of the intervention and non-intervention group. Baseline variables to be compared include age, sex, comorbidities, number of siblings, smoking in household, study site and speciality of health worker.

7.19 Analysis of main outcomes

The main superiority outcome of antibiotic reductions at day 14 will be assessed by a multivariate logistic regression model and results presented both as odds ratio and as the absolute risk difference of antibiotic exposure in the two study arms. This analysis will be done as intention to treat (ITT).

The main non-inferiority outcome of patient safety will be assessed by a multivariate, generalised, linear model to calculate an adjusted 95% confidence interval (CI) for the

COORDINATE

difference between CRP-guided and standard therapy in the number of days until recovery. This analysis will both be done as ITT and per-protocol (PP).

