Follow-up with Phone Calls

There will be no scheduled follow-up visit at the health clinic required by the study. Parents/caregivers will be phoned 3, 7 and 14 days after the index consultation to record outcomes. Phone calls will be blinded and performed by another AI (see appendix D):

- Number of symptomatic days after the consultation;
- Duration of specific symptoms;
- Return to school/work and usual activities;
- Additional contacts with HCWs;
- Any medicine bought over-the-counter or prescribed by other HCWs including the name of the drug(s);
- Additional diagnostic testing, including SARS-CoV-2 and outcomes;
- Complications (hospitalisation -days in hospital, ICU, medication/oxygen/ventilation received there-, pneumonia, death);
- Infections in their households;
- General well-being;
- Diarrhea

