9.4 Temporary halt and (prematurely) end of study report

The collaborating parties must immediately be informed in case of a temporary halt of the study or prematurely end of study including the reason(s) of such an action.

The PI will notify the collaborating parties of the end of the study within a period of 8 weeks. The end of the study is defined as the last patient's follow-up phone call.

Within one year after the end of the study, the investigator will submit a final study report with the results of the study, including any publications/abstracts of the study, to the collaborating parties and relevant sponsors.

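### Does the safety analysis fail because 7.19 sets no value for a child still ill, or dead, at the day-14 call?

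*Combined protocol and SAP*

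**What the plan says.** Section 7.19 states that the non-inferiority outcome "will be assessed by a multivariate, generalised, linear model to calculate an adjusted 95% confidence interval (CI) for the" "difference between CRP-guided and standard therapy in the number of days until recovery", both by intention to treat and per protocol. Section 7.16 puts the margin on the mean: "the intervention arm is allowed to have a mean time to recovery that is one day longer" than in the control arm. It sizes the comparison from this statement: "The duration of acute respiratory tract infection in children is approximately 7 days with a standard deviation of 5 days". No 14-day limit is mentioned there.

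Observation is limited to 14 days. Under 7.5, "Parents/caregivers will be phoned 3, 7 and 14 days after the index consultation to record outcomes", and 9.4 adds: "The end of the study is defined as the last patient's follow-up phone call". Among the items collected at the calls are "Number of symptomatic days after the consultation" and "Return to school/work and usual activities".

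Three other sections bear on the point. Section 7.12 analyses every enrolled child in the randomised group. Section 7.20 uses inverse probability weighting (IPW) for missing data and loss to follow-up. Sections 7.15 and 7.21 make hospital admission, reconsultation and mortality separate secondary outcomes.

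**The concern.** A model for days until recovery needs a number for every child. A child reached on day 14 and still ill has no observed recovery day, and a child who has died never will. Neither 7.19 nor 7.20 says what to enter.

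Two codings are conceivable. The child may be entered as 14, which limits the outcome to 14 days. Or the child may be left without a value and handled through the weighting as if missing. Both shrink a true difference when the CRP arm is slower, the second much more. Since this outcome carries the safety claim, a shrunken difference favours declaring non-inferiority. The margin has a matching ambiguity: it was sized with the full-duration SD of 5 days, while the data can supply only a 14-day mean.

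**Working it through.** **The plan's own figure.** Inputs from 7.16: margin 1 day, SD 5, power 90%, significance level 0.05. Assumed: true difference 0 and a one-sided level of 0.05. Then n per arm = 2 × (1.645 + 1.282)² × 5² / 1² = 428.2, rounded up to 429, or 858 in total. This matches the plan and confirms that the sizing used an SD with no 14-day limit.

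**Inputs for the check.**
- Analysable children per arm: 1204 × 0.85 / 2 = 512 (target and dropout from 7.16).
- Recovery time from consultation: mean 7, SD 5, gamma or log-normal. This is an assumption, because 7.16 gives 7 and 5 only as the duration of illness.
- Truth: the CRP arm is 1 day slower in full duration, either with proportional slowing (SD rises to 5 × 8/7) or with a constant SD of 5.
- Test: unadjusted difference in means; non-inferiority if the upper 95% limit is below 1 day.

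**Formulas.** With S(t) the share still ill at time t, the 14-day mean is the integral of S(t) from 0 to 14. The second moment is the integral of 2t·S(t) over the same range. With D the difference in 14-day means and SE = √[(SD₁² + SD₂²)/512], the chance of declaring non-inferiority is Φ((1 − D)/SE − 1.96).

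**Entering 14.** The share of controls still ill after day 14 is 9.3% (gamma) or 8.1% (log-normal), and the control SD on the 14-day scale is 4.00 or 3.63.

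| Slowing | Shape | D (days) | SE | Non-inferiority declared |
|---|---|---|---|---|
| Proportional | gamma | 0.716 | 0.256 | 19.8% |
| Proportional | log-normal | 0.742 | 0.232 | 19.8% |
| Constant SD | gamma | 0.916 | 0.247 | 5.2% |
| Constant SD | log-normal | 0.921 | 0.225 | 5.4% |

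For the first row, (1 − 0.716)/0.256 − 1.96 = −0.85, and Φ(−0.85) = 0.198.

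**Shorter times from consultation.** With an assumed mean 5 and SD 4, the rates are 3-12%. With mean 4 and SD 3, they are 2.5-7%.

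**Leaving unrecovered children out** (unweighted approximation, 7/5). D falls to 0.41-0.51 day (proportional) or 0.81-0.82 day (constant SD). Non-inferiority is declared in 68-73% or 13-15% of trials. Over the assumed 5/4 and 4/3 cases the range is 3-56%.

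**Reading the margin on the 14-day mean.** The error rate at the margin is then 2.5% by construction. One day on that scale equals 1.37-1.43 days of full slowing (proportional) or 1.09 days (constant SD), and the unrecovered share rises from 8-9% to 11-16%. With SD 4.00 and a one-sided 2.5% level, n per arm = 2 × (1.960 + 1.282)² × 4.00² = 336.2, so 674 in total; the log-normal SD gives 556. With 512 per arm and equal arms, power is 97.9% or 99.3%.

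**Which coding the text supports.** The count in 7.5 is of symptomatic days after consultation. A child reported still ill at the last call therefore has a recorded count of about 14. Section 7.12 keeps that child in the analysis. Section 7.20 does not take the child out, because a child who was reached and reported ill is neither missing nor lost. Leaving the child without a value runs against all three sections.

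**The case for a change.** The strongest case for a change is that two unwritten codings give very different error rates (about 5-20% against 13-73% in the 7/5 illustration), that this outcome decides the safety claim, and that 7.12 has the investigators do the analysis. On that view the rule should be fixed before anyone sees the data. Moreover, one day on the 14-day mean is a more lenient claim than one day of full duration, and a reader should know which is meant.

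Part of this stands. No sentence states the value, and no sentence ties the margin to 14 days. For deaths the symptom-day count does not fill the gap either. The documents give no expected death rate, so no size can be attached to that part; deaths are at least reported as an outcome of their own.

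The rest does not carry a change. The damaging coding requires reading 7.5, 7.12 and 7.20 against their plain sense. The 5-20% belongs to the coding that a clarification would itself adopt: 14 entered, same model, same margin. Accept-or-reject decisions would be identical with or without the added sentence. Section 7.17 also places data checking before unblinding, so the coding of these children can be settled without knowledge of the arms. The lenience of the 14-day scale is a matter of stating the claim as one about 14 days, which the length of follow-up already makes plain.

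**Conclusion.** No change is called for. This is missing detail that an analyst fills sensibly by entering 14 for a child still ill at the last call, and the resulting comparison is valid for mean days to recovery within 14 days. With equal arms this coding introduces no bias. On the 14-day scale the error rate at the margin is nominal and power is about 98-99% with 512 per arm, so the sizing with SD 5 errs on the safe side.

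The 5-20% applies only if the margin is meant as one day of full duration, the CRP arm is truly one day slower, and the 7-day mean and SD of 5 run from consultation. It falls to 2.5-7% at an assumed 4/3. The figures also assume gamma or log-normal times and an unadjusted comparison of means; 7.19 names no family or link for its model. How recovery is recorded may be set out in the phone questionnaire, whose content is not in the supplied text.
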